**By mail and phone:**

Potential participants will be mailed a letter describing the study with a phone line to call if they do not wish to participate. Those who do not decline will be called by our Survey Research Program staff. The Survey staff will obtain oral consent to be screened for eligibility by phone, answer any questions about the study, screen for eligibility, and, if eligible, obtain oral consent to wear the activPAL prior to the Baseline visit. Those who consent to participate in this stage will be scheduled by the Survey team for their Baseline measurement session. At 6 and 12 months, participants will receive an activPAL device and questionnaire by mail, and will participate in a follow-up in-person measurement visit (see In Person section below).

For participants in both the intervention i-STAND group (Group A) and the Healthy Lifestyles group (Group B), additional activPAL measurements will be collected (via mailed activPAL) at 3

months; for those *re-randomized* to the i-STAND booster group, they will also receive an activPAL at 9 months via mail. Neither the 3 or 9 month activPAL wears will be followed by an in-person visit. Reminder letters for upcoming in-person visits will be sent one-week prior to visit by the Research Specialist. For each period that an i-STAND subject wears an activPAL device, they will also receive a copy of their feedback chart via mail or in-person (depending on timepoint). If requested by the participant, reminders may be sent by email. Email addresses will be collected on the Contact Sheet if this request is made. Also see Supplement B.

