The subject will be informed that at any time they can choose to withdraw consent.

Consent will not be documented in their EMR.

*Note: in the consent form, we do not describe the standing desk, which is only offered to the i-STAND cohort, because:*

1. *This will be offered as a supplemental tool to support the standing intervention, which is the i-STAND intervention and will not be offered to the Healthy Living group*
2. *We do not want those randomized to the Healthy Living group to feel as though they have been given a lesser program simply because they are not given these support devices (they are being given a different program, that doesn't focus on standing).*
3. *The desk is not part of the intervention and people are not being required to use it, (neither are they required to use the Fitness device) but mentioning it might create greater disappointment among people assigned to the control arm, leading to differential attrition and undermining our analytic power and scientific integrity of the study. The fact that we observed this in the pilot support this as a realistic scientific concern that needs to be managed appropriately.*

**COVID-19 UPDATE:** As of Package 32, we are also offering an oral consent to participants to permit us to send them a blood pressure monitor via a third party vendor. Oral consent script is included in Package 32.

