COVID-19 UPDATE: We have created an Addendum to Consent oral script to offer participants the option to continue coaching past the protocol timepoint as dictated in the original consent form until they are able to complete their remote 6 or 12 month assessments (for those receiving the booster intervention). The majority of participants will only have 10 coaching sessions and a subsection of i-STAND cohort will receive booster sessions. This is to ensure that participants are still working on their study goals up until their outcome measures can be assessed. For those who have already completed a 10th call, the coach will reach out by phone and ask if they are interested in optional additional coaching. If the participant is interested, the coach will use the oral consent process. For those who have not yet had this 10th session and have one forthcoming, the coach will ask at the end of that call if they are interested in optional additional coaching and use the oral consent process.

COVID-19 UPDATE: We have created an Addendum to Consent oral script to offer participants the option of receiving a blood pressure monitor (to keep) which we will send by a third party vendor. The oral consent is to verify their permission to share their mailing address and name with a third party in order to mail the device. Participants can choose not to allow this, in which case we will not collect their blood pressure data in the remote measurement visit.

REMOTE (phone) COHORT

No addendum consents will be implemented at this time with any newly recruited participants into the Remote Cohort. The additional coaching option will not apply to this cohort and the consent to give their name/address to a third party is covered in the screening that occurs during recruitment by the survey research group.

2022 BUDGET CUT UPDATE:

As of March 31, 2022, and upon approval of this IRB submission (Package 58) we will be mailing an Informational Letter to participants in both cohorts advising them of the change to the study and providing them a phone number to call if they have concerns. These letters will be sent in lieu of a revised consent form. In the letter we will highlight:

- Removing the 12-month visit which means \$30 less than they originally thought they'd receive for participation
- There is no change to risk
- There will be no potential for additional coaching beyond 6-months (only offered to a subset of the participant population)

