  - a. All i-STAND participants will receive one more in-person session and 8 follow-up phone calls (10 contacts total) from their health coach over 6 months. All participants will also be sent an activPAL to wear, as well as a survey, at the mid-point (Month 3) and will receive a \$20 incentive for wearing the activPAL at month 3. All participants will receive a reminder phone call from the RS to confirm receipt of the packet containing the activPAL and the survey. If the packet was not received, the RS will resend another packet. At the 3-month mark, health coaches will also collect satisfaction data on use of the devices. This information will be collected over the phone and input into REDCap by the coaches, so as to avoid contaminating the survey data collected by the blinded research specialists, who will be managing the primary survey distribution and data collection.
  - b. All Healthy Lifestyle Control Participants will receive 9 follow-up phone sessions after their initial in-person session (10 contacts total). Each call will cover a topic of interest to the participant (see Table 4). Relevant content from the Healthy Living workbook will be briefly reviewed and goals will be set. Follow-up calls will check-in with prior calls. The calls will occur every 2-3 weeks over the first 6 months of the study.
  - c. COVID-19 UPDATE: both i-STAND and Health Lifestyle participants will be offered, using an Addendum to Consent oral agreement, the option of additional coaching calls beyond the 10 sessions to occur on a monthly basis. See page 15 of this protocol for details and see the Addendum Consent for script. 3-month assessments will also still be mailed. A study RS will assemble packets with charged activPALs and participant surveys at their home and mail to participants via the USPS. Study RS has sanitation procedures that are used at the office that will also be used at home in assembling packets (gloved, wipes, etc). Participants will mail the packets back to KPWHRI and a study RS will be checking our mailbox once a week for returned devices/surveys.
  - d. All participants (i-STAND and Healthy Lifestyles control group) will attend a 6-month measurement visit. A few weeks prior to the visit and to mailing the activPAL device to the participants, the RS will call the participant to ensure we have accurate contact information and to remind them of the upcoming timepoint. If the participant has

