requested that scheduling visits/reminders of visits be done via email, this information will be sent via email from the RS. The same measurements and assessments will be taken as at baseline except a study satisfaction questionnaire will be included in the self-reported survey. All participants will receive a \$40 incentive for completing measurements at the 6 month visit. For those participants who do not show up to their scheduled 6-month visit, we will attempt to reach them by phone and then by mail, encourage their participation and completion of this timepoint. At this in-person visit, if participants inquire about their blood values or blood pressure, we will share the information with them but without interpretation and advise them to see their provider if they have questions or concerns. After completing the 6-month measurement visit, all I-STAND participants will be re-randomized to EITHER receive i-STAND booster sessions (5 additional phone contacts) or no further intervention for 6 months. The health coach will call each participant after they complete their 6 month measurements to inform them of their assignment.

- COVID-19 UPDATE: We will be ordering and sending directly to individual participants from a third party vendor (pending oral consent from participants) Omron BP Monitors (The Omron 3-Series BP7100 model) for any 6 and 12-month measurements. Participants will not be expected to return this device. Instructions will be included in the mailed packet that also includes the survey, activPAL, paper measuring tape (Medline 72" paper measuring tape). RS staff will call participants to conduct the chair-sit measurement and to verbally collect the BP/weight/waist measurements from participants. As usual, study packets mailed to participants will include return envelopes for the activPALs and the surveys.
- We will send incentives to participants when business returns to normal and we are able to send cash incentives. Participants will be notified that they will receive their incentives at a later time.
- We have amended Supplement B to request permission to use email to send the link for the survey (REDCap) to participants for whom we have email addresses and who have given us permission to contact them using email.
- We will track those participants who receive a device from a third party vendor on the internal PHI Disclosure Tracking Form (<https://ghriweb01.ghc.org/disclosuretrack/seldisc1.aspx>)

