**a. Data Analysis**

Describe the data analysis plan, including:

- Statistical procedures.
- When applicable, the power analysis.
- Any procedures that will be used for quality control of collected data.

FOR BOTH ORIGINAL AND REMOTE COHORTS: We will add secondary analyses to address changes due to COVID-19.

*Preliminary analyses. The statistician will be blinded to intervention condition and intent-to-treat analyses will be performed.* Before analysis, data will be cleaned and checked for out-of-range and invalid values. We will examine the distribution of baseline covariates across groups to evaluate balance by randomization assignment. Further, we will compare follow-up rates by group assignment along with assessing for imbalance of baseline covariates by intervention group in the subset with follow-up outcome measures. Given the large sample size, we expect that between-group differences will be small. However, if factors differ by group at baseline, we will adjust for them in the final analyses or use them in imputation analyses if we have a larger than expected dropout rate. All analyses will be based on the “intent-to-treat” principle. Regardless of actual intervention participation, outcomes will be analyzed using the group to which participants were randomly assigned. We will also attempt to obtain follow-up data from all participants, regardless of participation level.

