**Aim 1: Determine the efficacy of i-STAND to improve primary and secondary outcomes at 6 months.**

*Primary Outcome Analysis:* Our primary outcomes are change from baseline in mean daily sitting time and systolic and diastolic blood pressure (described in Section C12). We will compare group means for our primary outcomes between participants randomized to i-STAND versus attention control using linear regression with generalized estimating equations (GEEs) including both outcome time points at 3 and 6 months. GEE is used to account for multiple outcomes measured on the same study participant along with relaxing the normality assumption that standard linear regression methods require. We will adjust for baseline covariates including participant age, sex, physical function, and respective baseline outcomes with other covariates that are imbalanced in preliminary analyses. If dropout is above 15%, we will employ imputation techniques to address missing data issues. However, our focus will be on minimizing dropout rates. Analyses for secondary outcomes including lipids, fasting glucose, weight, and waist circumference will be similar, adjusting for respective baseline outcomes in the analysis. *Aim 2: Determine the maintenance of sitting and blood pressure reductions over 12 months.* We will conduct a sequential series of analyses using a similar statistical framework as outlined for Aim 1, but using 12-month follow-up data. We will first run a regression model with three groups (attention control, i-STAND no boosters, and i-STAND with boosters) including baseline covariates as outlined above. We will then

assess differences in primary outcomes at 12 months in the two i-STAND groups: with and without the booster intervention. If a significant difference in a given primary outcome is found in sitting time at 12 months between the i-STAND booster versus no booster groups (Scenario 1), we will further compare the i-STAND booster and no booster groups to the attention control group. Scenario 1 assessments will determine if i-STAND with boosters is better than i-STAND without boosters and if either or both I-STAND groups are better than attention control at 12 months.

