**Power calculations.** Our sample size of 284 ensures 90% power to detect a difference in the reduction of sitting time between i-STAND and attention control of 41 minutes at 6 months (primary time point). Given our pilot results and i-STAND's long-term goal target of a 2 hour reduction in sitting time, a difference in sitting time reduction of 41 minutes is achievable. We assumed a standard deviation (SD)

in change in sitting time of *97 minutes/day based on I-STAND pilot RCT data*, a pooled sample t-test, and a 15% loss to follow-up under which we would observe 241 participants at 12 months. *Further, this sample size provides 90% power to detect a difference of 6.2 mmHg change in systolic (14.7 SD) and 4.0 mmHg change in diastolic (9.5 SD) blood pressure. We are powered for comparable reductions in blood pressure as those observed in walking and exercise interventions (5-10 change in systolic and 1-6 mmHg change in diastolic blood pressure). Therefore, we are powered to achieve a minimal clinically important difference for blood pressure outcomes.*

For Aim 2, we will have 90% power to detect a 58-minute difference in sitting time between i-STAND with boosters compared to i-STAND without boosters at 12 months. Further, given Scenario 2 in which i-STAND boosters is not different than i-STAND without boosters we will have 90% power to detect a 41-minute difference in sitting time with combined I-STAND groups. Given Scenario 1, in which i-STAND with boosters is significantly different from i-STAND without, at 12 months, we will have 90% power to detect a 50-minute difference in sitting time between either i-STAND group and the attention control. *For blood pressure outcomes, we have 90% power to detect an 8.8 mmHg change in systolic blood pressure and 5.7 mmHg change in diastolic blood pressure when comparing i-STAND groups (booster vs. no booster) at 12 months.* Therefore, this study is well powered to address all aims.

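### Imputation is planned only above 15% dropout, the loss the trial was sized for; at or below it the primary 6-month comparison has no stated missing-data assumption, working correlation or sensitivity analysis

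*Combined protocol and SAP*

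**What the plan says.** Section 5.a (Data Analysis), Aim 1, specifies a linear GEE on the 3- and 6-month outcomes, adjusted for age, sex, physical function, the baseline value of the outcome, and covariates found to be imbalanced. On missing outcomes it says: "If dropout is above 15%, we will employ imputation techniques to address missing data issues". The preliminary-analyses paragraph agrees: factors that differ at baseline will be adjusted for, or the team will "use them in imputation analyses if we have a larger than expected dropout rate".

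The power paragraph assumes "a 15% loss to follow-up under which we would observe 241 participants at 12 months". The label is 12 months, although the same paragraph makes 6 months the primary time point.

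Dropout is not defined by arm, visit or outcome. Above 15%, the method is given only as imputation, with a citation (reference 52) whose title concerns non-ignorable non-response.

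Three procedural points bear on this:
- Section 4.l explains why the standing desk is left out of the consent form: "mentioning it might create greater disappointment among people assigned to the control arm, leading to differential attrition". It adds that this was seen in the pilot.
- Under the COVID-19 update in section 4.o, Original-cohort participants may decline the mailed monitor, "in which case we will not collect their blood pressure data in the remote measurement visit".
- In the Original cohort, month 3 is a mailed activPAL and survey. Section 4.j states: "Neither the 3 or 9 month activPAL wears will be followed by an in-person visit". No month-3 blood pressure is described for that cohort.

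**The concern.** The rule switches missing-data handling off at the loss the trial expects. A percentage is not a sound criterion. Ten per cent loss can bias the comparison if poor responders leave one arm, while 20% loss that is alike in both arms may do little harm.

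The unstated working correlation matters here. If dropout before month 6 depends on month-3 response, an independence GEE with group-by-visit terms compares the observed 6-month means, which are distorted when the mechanism or the rate differs by arm. A non-independence structure borrows from month 3 and largely corrects this where month 3 was measured. Neither handles dropout tied to the unseen 6-month value, which only a sensitivity analysis can probe.

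Blood pressure, also a primary outcome, is more exposed. It can be missing without dropout when the monitor is declined, and the Original cohort (100 of the planned 284) has no described month-3 value to borrow from.

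**Working it through.** **1. The plan's own figure.** Inputs from the power paragraph are difference 41 min, SD 97 and power 90%. Alpha is not stated; I take 0.05 two-sided.

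n per arm = 2 × (1.960 + 1.282)² × (97/41)² = 21.0 × 5.60, which rounds up to 118, or 236 in total. 236/0.85 = 278, close to 284. In reverse, 284 × 0.85 = 241, and a pooled t-test on 241 has 90.5% power. The sample size stands.

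**2. Where the trigger falls.** 42/284 = 14.8% triggers nothing and 43/284 = 15.1% does, if dropout means overall loss.

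**3. Illustration for sitting time.** From the plan: effect 41 at month 6 and SD 97. Assumed:
- month-3 effect 54, and 3/6-month correlation 0.6;
- a baseline covariate correlated 0.4 with change;
- 15% average loss at month 6, month 3 complete;
- odds of loss rising 1.5-fold or 2.7-fold per SD of poorer month-3 change;
- group-by-visit terms (not spelled out in the plan) and independence correlation.

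The unadjusted estimates are large-sample simulations (600,000 per arm). Let d be the shift, in SDs, of the month-3 mean among those still seen at month 6. The bias in an arm's 6-month mean is 97 × 0.6 × d unadjusted and 97 × (0.6 − 0.4 × 0.4) × d = 97 × 0.44 × d adjusted. Adjustment therefore keeps 0.44/0.60 = 0.733 of the shift, and the adjusted columns are 41 + 0.733 × (unadjusted − 41).

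| Who leaves selectively (i-STAND/control loss) | Unadjusted, odds 1.5 | Unadjusted, odds 2.7 | Adjusted, odds 1.5 | Adjusted, odds 2.7 |
|---|---|---|---|---|
| i-STAND only (15%/15%) | 44.4 | 48.5 | 43.5 | 46.5 |
| i-STAND only (20%/10%) | 45.4 | 51.0 | 44.2 | 48.3 |
| Both (20%/10%) | 43.2 | 45.7 | 42.6 | 44.4 |
| Both (10%/20%) | 38.7 | 36.0 | 39.3 | 37.3 |
| Control only (15%/15%) | 37.4 | 33.2 | 38.4 | 35.3 |
| Both (15%/15%) | 41.0 | 41.0 | 41.0 | 41.0 |

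Direct simulation with the covariate agrees, at 38.3 to 44.3 and 35.1 to 48.2. Allowing for simulation error, I read these as about 38 to 44.5 and 35 to 48.

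**4. Against the standard error.** Unadjusted: 97 × √(4/241) = 12.5. Adjusted: 12.5 × √(1 − 0.4²) = 11.5. The largest adjusted shift is (48.2 − 41)/11.5 = 0.63 standard errors at odds 2.7. At odds 1.5 it is (44.5 − 41)/11.5 = 0.30.

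**5. What a missing-at-random method recovers.** Take i-STAND-only selective loss (20%/10%) at odds 2.7, with the covariate. The estimate is 40.9 if month 3 is observed for all leavers, 44.2 if half leave before month 3, and 48.7 if all do. The last is no correction, within simulation error.

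**The case against.** The plan does not ignore missing data. It compares follow-up rates by arm, checks baseline balance among those followed up, adjusts for baseline, and seeks data from everyone. For a missed 6-month visit in the Original cohort, "we will attempt to reach them by phone and then by mail, encourage their participation and completion of this timepoint"; the Remote cohort has a similar step, and people who withdraw are asked whether they will still be measured. An analyst might also choose an exchangeable correlation, which alone brings the unadjusted patterns above to 40.5 to 41.3. All this stands. It reduces the problem, and it makes naming the correlation the smallest useful repair. It does not address dropout tied to response after baseline, and an unstated choice cannot be relied on. The COVID-19 secondary analyses are mentioned without content.

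Three stronger readings are tempting, and the documents do not support them:
- *The unadjusted range of 33 to 51 minutes, about 0.8 standard errors, is the size of the problem.* The plan adjusts for the baseline outcome, so the adjusted figures apply.
- *The consent note predicts this bias, with understated benefit and lost power.* The note describes disappointment at being allocated to control. It supports concern about unequal attrition, not dropout driven by month-3 change, and such loss could well come before month 3.
- *The plan has no missing-data assumption at all.* Above 15% it cites a paper whose title points to non-ignorable non-response. The gap is firm at or below 15%.

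**Conclusion.** The concern holds as a gap in specification with modest likely consequences. At or below the loss the trial was sized for, whether the 6-month comparison is unbiased rests on choices the plan leaves open, and the rule that switches imputation on is not tied to what causes bias.

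For sitting time, the shift after baseline adjustment is at most about 0.3 standard errors under weak dependence and 0.6 under strong dependence, in either direction, and about zero when mechanism and rates match across arms. These figures rest on the assumed correlations, loss patterns and independence structure. They are not predictions.

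A reader might infer that imputation or an exchangeable correlation would remove the bias. That is so only for leavers with month 3 measured; for earlier loss the correction is partial or absent. The blood pressure effect is not quantified here, and the sitting-time figures should not be carried over to it. The sample size is unaffected.

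**What to change.** Delete the 15% trigger. For each primary outcome, prespecify one method valid under missing-at-random, used at any dropout rate and drawing on the 3-month value where measured. Either of these would do:
- multiple imputation by arm, using baseline, the 3-month outcome, stratification factors and cohort; or
- a likelihood-based repeated-measures model with group-by-visit terms and unstructured covariance.

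If GEE is kept, state a non-independence working correlation.

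Add a delta-adjusted sensitivity analysis with arm-specific shifts over a range the study team justifies. This also covers loss before month 3 and blood pressure without a month-3 value. Report missingness by arm, visit and outcome, so that declined monitors are visible.

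The cost is SAP wording and modest programming, with no new data. With 15% loss unrelated to outcome and month 3 observed, the unadjusted standard error for sitting time is 12.2 min under missing-at-random against 12.5 for observed data only, so no precision is lost in that setting. The downsides are reliance on the imputation or covariance model and a judgement about the delta range.

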## Data, sources, and date range

The following table shows how outcomes data will be collected

Source (specify) (i.e., from KPWA, or from an existing or previous study)	Key Information/Description of Variables	Date Range
---	--	------------

activPAL activity monitor	PRIMARY OUTCOME 

• Change in mean daily sitting at 6 months

	Baseline to 6-months
ORIGINAL COHORT: In-person measurement visit at KPWHRI  COVID-19 UPDATE AND NEW REMOTE COHORT REMOTE MEASUREMENT	PRIMARY OUTCOME 

• Change in systolic and diastolic blood pressure

	Baseline to 6-months
In-person measurements collected at clinic visit at KPWHRI  COVID-19 UPDATE AND NEW REMOTE COHORT: REMOTE MEASUREMENT OF WEIGHT	SECONDARY OUTCOMES 

• Change in HbA1c (Original Cohort only)

• Change in Weight

	Baseline to 6 months
In-person measurements collected at clinic visit at KPWHRI  COVID-19 UPDATE and REMOTE COHORT: REMOTE MEASUREMENT OF WEIGHT and BP	OTHER EXPLORATORY OUTCOMES for i-STAND BOOSTER ONLY 

• Change in HbA1c (original cohort only)

• Change in Weight

• Change in systolic and diastolic blood pressure

	Baseline to 12 months
activPAL activity monitor	OTHER EXPLORATORY OUTCOMES for i-STAND BOOSTER ONLY 

• Change in time spent sitting or lying down

• Change in step counts

	Baseline to 12 months
Participant questionnaire	OTHER EXPLORATORY OUTCOMES 

• Change in quality of life

• Change in depressive symptoms

	Baseline to 6 months

	
 
• Change in physical function
 
	
VDW	
Various chronic conditions (e.g. diabetes, cardiovascular conditions); lab values for HbA1c, cholesterol; blood pressure; blood pressure medications; height and weight; medical events (e.g. falls, hospitalizations, heart attack, stroke, blood clots); and, healthcare costs.
	
One year prior to first Study Visit date to the end of the study for up to 5 years after the study ends, no later than June 1, 2028

**2022 BUDGET CUT UPDATE:** As of March 31, 2022, neither the i-STAND cohort nor the control cohort will have a 12-month assessment to collect the outcomes listed in the table above. To be as clear as possible - those items have been highlighted in green.

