If i-STAND groups do not differ at 12 months (Scenario 2), we will combine i-STAND groups and run a second regression model on each 12-month outcome including only attention control and i-STAND. If this regression shows that i-STAND has lower sitting time and/or blood pressure than attention control, we will conclude that the i-STAND intervention improved sitting time and/or blood pressure over 12 months, but boosters were not shown to be efficacious. We will conduct a similar analysis for secondary cardiometabolic risk marker outcomes.

**2022 BUDGET CUT UPDATE:** As of March 31, 2022, neither the i-STAND cohort nor the control cohort will have a 12-month assessment, so we are removing Aim 2. However, we will still explore maintenance of sitting and blood pressure reductions over 12-months for future grants and pilot data purposes.

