**2022 BUDGET CUT UPDATE:** As of March 31, 2022, for Aim 2, assuming we have 124 participants completing 12-month outcome follow-up, we will have 90% power to detect a 81-minute difference in sitting time between I-STAND with boosters compared to I-STAND without boosters at 12 months. Further, given Scenario 2 in which I-STAND boosters is not different than I-STAND without boosters we will have 90% power to detect a 57-minute difference in sitting time with combined I-STAND groups. Given Scenario 1, in which I-STAND with boosters is significantly different from I-STAND without, at 12 months, we will have 90% power to detect a 70-minute difference in sitting time between either I-STAND group and the attention control. For blood pressure outcomes, we have 90% power to detect an 12.3 mmHg change in systolic blood pressure and 8.0 mmHg change in diastolic blood pressure when comparing I-STAND groups (booster vs. no booster) at 12 months. We acknowledge we will likely be underpowered for Aim 2 and this is why we have now made it exploratory.

b. Sharing of Results with Subjects

Describe whether results (study results or individual subject results, such as results of standard or research lab tests and genetic tests) will be shared with subjects or their providers.

If the study carries a risk of incidental findings, describe your plan for evaluating these and determining whether and how subjects or their providers will be given this information.

If laboratory results will be shared with subjects or their healthcare providers, verify that the laboratory conducting the test is Clinical Laboratory Improvement Amendments (CLIA) certified.

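### The exploratory booster contrast is randomised after month 6, but its model omits the month-6 outcome, which costs precision without causing bias

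*Combined protocol and SAP*

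**What the plan says.** The second randomisation is described in section 5, Study Procedures, Original cohort, item 3d: "After completing the 6-month measurement visit, all I-STAND participants will be re-randomized to EITHER receive i-STAND booster sessions" or no further contact. Item 5d for the Remote cohort says the same.

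The analysis of the resulting groups is under Aim 2 in section 5.a, "using a similar statistical framework as outlined for Aim 1, but using 12-month follow-up data". It begins with a "regression model with three groups (attention control, i-STAND no boosters, and i-STAND with boosters) including baseline covariates as outlined above". The covariates meant are those given for Aim 1: "We will adjust for baseline covariates including participant age, sex, physical function, and respective baseline outcomes", together with any found imbalanced in the preliminary analyses. No section names the month-6 outcome as a covariate for the booster contrast.

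The status of the contrast changed in March 2022. Section 1 cuts Aim 2. The update after the Aim 2 analysis removes it as an aim but adds that "we will still explore maintenance of sitting and blood pressure reductions over 12-months for future grants and pilot data purposes", without naming boosters or a model. The update to the power calculations does name booster versus no booster. It restates the detectable differences with 124 completers and acknowledges that "we will likely be underpowered for Aim 2 and this is why we have now made it exploratory". That last update is the text that keeps the contrast alive.

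**The concern.** For booster versus no booster, the moment of randomisation is month 6. The outcome measured then is a legitimate pre-randomisation covariate. It is also nearer in time to the 12-month outcome than the enrolment value is, so one would usually expect it to predict that outcome better. Leaving it out keeps in the error term any variation that month 6 explains and enrolment does not.

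The groups are small. If the month-6 standard deviation is about 97 min (assumed), the standard error of a chance month-6 difference between two groups of 31 is 97 × √(2/31) = 25 min. Section 5.a expects small between-group differences because the sample is large, and that reasoning does not carry over to groups of 31.

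Two things are at stake. Under the Aim 2 rule, the i-STAND groups are pooled when they do not differ, and boosters are then reported as not shown to work; avoidable imprecision pushes towards that outcome. The remaining purpose is pilot information for later grants, and the value of that information depends on how precise the estimate is.

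**Working it through.** **Inputs from the documents (section 5.a, Power calculations and its 2022 update).** SD of change in sitting time 97 min/day; pooled t-test; 90% power; 124 completers at 12 months; 81 min detectable for booster versus no booster.

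**Inputs assumed.** Two-sided alpha 0.05 (not stated). Equal allocation, so 62 i-STAND completers and 31 per booster group. Equal SD at every visit. All visit-to-visit correlations.

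**Step 1: reproduce the plan's figure.** With a noncentral t, 31 per group and SD 97, the detectable difference is 81.2 min, against 81 stated. The companion figures also reproduce: 56.9 (stated 57), 69.9 (70), systolic 12.30 (12.3) and diastolic 7.95 (8.0). At this size, power is about 64% for the pre-cut 58 min and 37% for 41 min. The 81 min uses the unadjusted change SD, so it is not the planned covariate-adjusted analysis.

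**Step 2: formulas for the adjusted models.** Let r_b be the baseline–12-month correlation, r_6 the 6–12-month correlation and r_06 the baseline–6-month correlation.

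- SD at a visit: σ = 97/√(2(1 − r_b))
- Residual SD, enrolment baseline only: σ√(1 − r_b²)
- With both: R² = (r_b² + r_6² − 2·r_b·r_6·r_06)/(1 − r_06²), residual SD = σ√(1 − R²)
- Detectable difference = residual SD × 81.17/97 = residual SD × 0.837

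The last line keeps the two-group degrees of freedom and ignores the few used by covariates.

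**Step 3: one case in full.** Take r_b = 0.5, r_6 = 0.7, r_06 = 0.6.

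- σ = 97/√1 = 97
- Baseline only: 97 × √0.75 = 84.0, giving 70.3 min
- Both: R² = (0.25 + 0.49 − 0.42)/0.64 = 0.50; 97 × √0.50 = 68.6, giving 57.4 min
- Residual variance ratio: 0.50/0.75 = 0.67, a 33% reduction

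**Step 4: range.** r_b runs from 0.4 to 0.6, and r_06 is equal to r_b or 0.1 higher. Detectable differences are in minutes.

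| r_6 − r_b | Baseline only (planned) | Month 6 instead | Both | Variance cut from adding month 6 |
|---|---|---|---|---|
| 0 | 68–73 | 68–73 | 65–69 | 6–14% |
| 0.1 | 68–73 | 64–65 | 62–63 | 14–28% |
| 0.2 | 68–73 | 55–59 | 53–59 | 25–47% |

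An advantage of 0.3, the most favourable tried, gave 39 to 53 min with both covariates; the conclusion does not rest on it. Adding month 6 helped in every case. Substituting it for baseline gave nothing when the two correlate equally with month 12.

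**The case against.** **The aim was cut.** Two of the three updates remove Aim 2, and no trial conclusion now depends on this contrast. That limits the importance of the point but does not dispose of it: the power update still presents booster versus no booster as an exploratory comparison on data already collected.

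**The estimate may look invalid.** A reader might infer that the enrolment baseline is the wrong covariate, or that a chance month-6 difference biases the result. The documents do not support this. Enrolment values also precede the second randomisation, chance imbalance averages zero, and the standard error already reflects it. Only efficiency is lost.

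**The gain may look like 81 to 57 min.** It is not, because the plan already adjusts for baseline. In the worked case the relevant change is 70 to 57 min, and its size depends wholly on assumed correlations. Even 57 min exceeds the 54 min that the pilot RCT found for i-STAND versus control.

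**The outcomes table may look wrong.** Its rows headed "OTHER EXPLORATORY OUTCOMES for i-STAND BOOSTER ONLY" run from baseline to 12 months. Once month 6 is a covariate, taking change from month 6 as the outcome leaves the group contrast unchanged. Those rows also concern collection that the 2022 update ended.

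**The plan may already cover it.** The clause on imbalanced covariates does not name month 6. If the similar framework means GEE with month 6 as an outcome, the precision is still not recovered unless the booster groups are constrained to be equal at month 6, which is not stated.

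**Month-6 values can be missing or differ in method.** This stands. Under section 4.o, Original cohort participants could decline the mailed monitor, and their remote blood pressure was then not collected. In that cohort the clinic and home monitors also differ, so the correlation with month 12 could be higher or lower than that of baseline, depending on which visits were remote.

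**Conclusion.** The point holds as a matter of precision. The exploratory booster contrast omits the covariate measured closest to its own randomisation, and the planned estimate is unbiased but less precise than it could be. With 31 per group, equal SDs across visits and assumed correlations, adding month 6 to enrolment baseline lowers residual variance by about 6 to 14% at worst and 25 to 47% if month 6 correlates 0.2 more strongly with month 12. The detectable difference moves from 68–73 min to 53–69 min. These figures concern sitting time; no equivalent was computed for blood pressure.

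The improvement is modest. Across that range the contrast stays underpowered for 41 min, the difference the main comparison was sized for. The omission is certain from the text, but the size of the benefit is not. It is worth correcting because it costs little.

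**What to change.** In section 5.a, state that booster versus no booster will be estimated in a separate model restricted to re-randomised i-STAND participants. The 12-month value is the outcome. The covariates are the month-6 value and the enrolment baseline of that outcome, plus age, sex and physical function. Both outcome values should be included, since month 6 alone may gain nothing.

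Impute any missing month-6 covariate so that no one is dropped from groups of about 31. Using only data collected before re-randomisation for this keeps it a pre-randomisation covariate.

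Leave month 6 out of every i-STAND versus attention control model, including the three-group model. There it is post-randomisation, and adjusting for it would remove part of the i-STAND effect. The outcome definitions in the data-sources table need no change.

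The cost is a short addition to the plan, one extra model on data already held, and the handling of some missing month-6 blood pressures.
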